## 4 STUDY DESIGN

The study will be conducted in compliance with the protocol, the good clinical practice standards, and the provisions of the corresponding ethics committee.

This will be a randomized, open-label, controlled, multicenter, exploratory Phase II study of efficacy. Pregnant patients with a single fetus who after reading the informed consent voluntarily agree to participate in the study will be included.

For secondary outcomes, patients will be their own controls on the following endpoints to be tested: cervix anatomical features—position and length—; plasma and endometrial progesterone concentrations in non-pregnant menopausal women; surveys on pregnant women to establish the acceptability and tolerance of the intervention; and local and systemic safety issues.

4.1. Pregnant Volunteers: 270 + 10% pregnant women at risk of preterm birth from the 4 participating sites will be recruited. This population will be divided into 3 treatment groups with 90 participants each.

They will be informed and invited to participate in the study at prenatal and/or ultrasound control between 16 and 24 weeks of gestation. Volunteers will be included in all cases up to 24 (0/0) weeks of gestation. Volunteers will be selected on the basis of their clinical history and by transvaginal ultrasound performed between weeks 16 and 24. All volunteers with a single pregnancy and cervical length  $\leq 25$  mm but  $\geq 10$  mm will be invited to participate in the study. Prior to inclusion in the study, fetal vitality or other exclusion factors discussed in detail below will be confirmed. Those patients who do not agree to participate in the study will receive the current standard care at each participating site depending on their condition.

4.1.1. Inclusion criteria in pregnant volunteers:

- Pregnant women with a single fetus with a cervical length of 10-25 mm between 16 and 24 weeks of gestation with no pre-existing risk factors.
- Women with ongoing pregnancy between 16 and 24 weeks of gestation with a single fetus and cervical length  $\geq 10$  mm, and having pre-existing risk factors in the immediately previous pregnancy characterized by:
  - Preterm birth before week 35 (with a viable fetus).
  - Premature rupture of membranes before week 35 (with a viable fetus).

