### 9.1. Sample Size

The calculation of the sample size is based on the power to detect differences in the proportion of spontaneous delivery before 32 and 34 weeks of gestation between the cerclage pessary formulations with respect to the control group (vaginal capsules containing 200 mg progesterone). Collecting data from at least 90 women in each group will provide a power of at least 80% to detect differences at a rate of 40% or more using a two-tailed test with  $\alpha=0.05$  for a non-corrected Chi square.

We estimate that up to 10% of enrolled women may not complete the study, so it is planned to enroll at least 99 pregnant women per group to reach at least 198 treated with the cerclage pessaries, and 99 treated with soft progesterone capsules as control group (i.e., 99 per vaginal formulation).

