### 9.2. Statistical analysis

For quantitative variables, descriptive statistics will be used (mean, standard deviation, minimum, median, maximum, 95% CI, and number of observations), whereas for categorical variables, frequencies and percentages analyses will be carried out. Results will be tabulated by treatment arm and pooled. The different vaginal formulations and progesterone will be formally compared. Results on efficacy and safety will be studied for each group separately and pooled, if relevant.

The proportion of women reporting adverse events during treatment will be cross-compared between the different doses using the Fisher's exact test or the Chi-square test.

All statistical analyses will be performed using the statistical software SPSS (Version 12) or Epistat 4.0.

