The sample size calculation is based on the power to detect differences in the proportion of spontaneous birth between 32 and 34 weeks of gestation, between the formulations of cerclage pessaries with respect to the control group (vaginal progesterone 200 mg capsules). Data collected of at least 90 women in each group will provide at least 80% of the power to detect differences with a rate of 40% or more, using a test of Chi-square of two tails with $\alpha = 0.05$ without correction.

We estimate that up to 10% of the enrolled women may not complete the study, so it must be planned to enroll at least 99 pregnant women in each group to reach at least 198 treated subjects with cerclage pessary and 99 subjects treated with soft capsules of progesterone as a control group (i.e. 99 per each vaginal formulation).

RANDOMIZATION

The randomization will be generated by an independent statistician. The program will be linked in sequential numbers with the code of randomized treatment. A qualified staff member of ANDROMACO laboratory will keep randomization codification, until the database is clean and ready for analysis. The treatment will be dispensed according to the randomization code, the women with unique pregnancy enrolled, will be randomized to receive one of the vaginal formulations of the study.

For the next volunteer, the site will have the next randomization number available. Each woman will receive only the formulation corresponding to the randomization number. The Investigator will record on the log the randomization number and the printed code on each formulation container. Each sites coordinator will assign the randomization code to the volunteers.

Subjects will be randomized to the following three study groups:

- Control Group (A): Intravaginal capsule of micronized progesterone 200 mg on a daily basis.
- Pessary Group (B): Pessary with 6.3 g of sustained release progesterone for a period of around 4 to 5 months.
- Pessary Group (C): Pessary with 7.7 g of sustained release progesterone for a period of around 4 to 5 months.

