5. ANALYSIS CONVENTIONS

The statistical analysis will be made by ILS Clinical Research under the authorization of Laboratorio Andromaco S.A.

GENERAL PRINCIPLES

The statistical analysis will be provided to give a general summary of the study subjects and a vision of the efficacy and safety of the results. The data provided by the sites will be summarized for this purpose. Tables of absolute and relative frequencies will be constructed for the quality variables. All the percentages will be presented with a decimal. The quantitative variables will be summarized with the number of subjects participating (n), mean, standard deviation (SD), and median, maximal and minimal.

Two tailed test will be carried out for all the analysis and the type I error is 0.05 for continuous variables and the discrete variables. All p values shall be rounded to three decimal and the values under 0.001 will be presented as <0.001 and values greater than 0.999 will be presented as 1.000. A comparison of the treatment groups will be done with respect to the demographic and baseline characteristics using inferential statistical techniques to detect if any of these variables may condition the results in the dependent variables. Comparisons in qualitative variables will be carried out using the Cochran-Mantel-Haenszel (CMH) test of general association, while the comparisons in quantitative variables will be made with a test of comparison of means (ANOVA analysis of variance) for independent samples with normal distribution. In the cases of no normality on the continuous variables, or in case of not belonging to the exponential family for discrete data, the parametric tests will be replaced for nonparametric tests such as Kruskal-Wallis or Friedman. These tests will be presented in each table as deemed necessary. All confidence intervals will be two-tailed and at 95%.

Table 1: Study Schedule of Assessments

Activities	Visit 1	Visit 2	Visit 3	Visit 4	Visit 5	Visit 6	Visit 7	Final Visit
Demography	X							
Medical History	X							
Physical Exam	X	X	X	X	X	X	X	X
Gynecological Exam	X							
Vital Signs	X	X ¹	X ¹	X ¹	X ¹	X ¹	X ¹	X ¹
Transvaginal Ultrasound	X	X ²	X	X	X	X	X	X
Pre-birth Control	X							
Obstetric Background	X							
Lab Tests (Blood and Urine)	X							
Eligibility	X							
Vaginal Discharge	X	X ³	X ³	X ³	X ³	X ³	X ³	X ³
Randomization	X							
Pessary Insertion	X							
Acceptability and tolerance to the insertion	X							X
Concomitant Medications	X	X	X	X	X	X	X	X

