10. EFFICACY ANALYSIS

STATISTICAL HYPOTHESIS

Null Hypothesis:

There is no difference between the methods of cerclage pessaries with a sustained release of 6.3 and 7.7 g of progesterone (Treatments B and C, respectively) with respect to the control method (Treatment A) for at least 20 weeks.

Alternative Hypothesis:

There is a difference between the Control Method (Treatment A) with respect to the one of cerclage pessaries with a sustained release of 6.3 and 7.3 of progesterone for a period of 4 to 5 months.

“There is a difference between the methods of cerclage pessaries with a sustained release of 6.3 and 7.3 g of progesterone (Treatments B and C respectively) with respect to the Control Method (Treatment A) for a period of 4 to 5 months”.

PRIMARY ANALYSIS

The primary objective is to evaluate the efficacy of two cerclage pessaries with doses of 6.3 and 7.7 g of sustained release micronized progesterone with respect to the standard treatment of 200 mg of progesterone in capsules administered daily. The primary efficacy analysis will be assessed by comparing the proportions of spontaneous premature delivery after 32 weeks but before 34 weeks of gestation, as primary results, among treatments through the CMH test. Also, the odds ratio and 95% confidence interval will be estimated, considering Group A as the control to be compared with groups B and C. Secondly, the comparison of proportions between the groups C and A will be done with the intention to confirm the significant difference between the highest dose and the standard treatment. Afterwards, the same comparison of proportions will be done with treatment B in order to establish the difference between the group of a minor dose and the standard. Finally the comparison between treatment B and C will be done hoping to demonstrate there is a difference of superiority between B and C where C must be minor than B regarding the number of low-risk pregnancies. The transitivity between treatments will be established according to the results. This is expected to be as follows:

$$\textit{Treatment C} < \textit{Treatment B} < \textit{Treatment A}$$

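### The SAP says the results will establish an order of the three treatments, but the trial is not sized to order the two pessary doses and plans no estimate of their difference

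*SAP*

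**What the plan says.** The SAP's letters are used here: A is the capsules, B the 6.3 g pessary, C the 7.7 g pessary.

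- **Tests (SAP section 10, Primary Analysis).** The three arms are first compared by CMH, then C with A, then B with A. The last step is: "Finally the comparison between treatment B and C will be done hoping to demonstrate there is a difference of superiority between B and C".
- **Ordering.** "The transitivity between treatments will be established according to the results". The expected order is displayed as C < B < A for the proportion at risk of preterm birth. No rule says whether an order rests on p-values or point estimates, or what follows a non-significant step.
- **Estimates.** Odds ratios with 95% confidence intervals are planned for B and C against A. None is planned for C against B.
- **Sizing (Protocol 9.1; SAP section 3 agrees).** Power is for differences "between the cerclage pessary formulations with respect to the control group". Ninety women per group "will provide a power of at least 80% to detect differences at a rate of 40% or more".
- **Error rate (SAP section 5).** "Two tailed test will be carried out for all the analysis and the type I error is 0.05", with no split across comparisons.
- **Pooling (Protocol 9.2).** "Results on efficacy and safety will be studied for each group separately and pooled, if relevant". No criterion is given, and the SAP contains no pooled pessary contrast.
- **Purpose.** The protocol's primary outcome (Synopsis and 7.1) is determination of the effective dose in the pessary. Both documents call the study exploratory.

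**The concern.** Significance in pairwise tests is not transitive. C versus A can be significant while B versus A and B versus C are not, and then no order of the three follows. An order read from point estimates always exists apart from ties, even when the two doses do the same thing.

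The ordering sentence therefore lets the report announce a ranking on either basis, and its hardest step, C against B, was never sized. Because dose determination is the stated primary outcome, that ranking would be the headline. A preference for one dose could rest on noise. A non-significant B versus C result could equally be read as showing the doses to be the same, with no interval to correct that reading.

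**Working it through.** **Inputs.** 90 evaluable women per arm (Protocol section 4), and a two-sided uncorrected chi-square at 0.05 (Protocol 9.1, SAP section 3). No event rate is given for sizing in any arm, so every rate below is an assumption. The CMH test has no stratification factor named and is treated as the ordinary 2-df chi-square.

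**1. The plan's own figure.** Read as a 40% relative reduction, with p̄ the mean of the two rates:

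power = Φ{ [|p₁ − p₂| − 1.96·√(2p̄(1−p̄)/90)] / √([p₁(1−p₁)+p₂(1−p₂)]/90) }

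At 51% v 30.6%: (0.204 − 1.96 × 0.0733)/0.0717 = 0.84, so power is 80%. Other control rates give 31% (at 20%), 64% (at 40%) and 85% (at 55%). The stated 80% is thus met for pessary versus capsules only if the capsule rate is about 51% or more. Read as 40 absolute points, 16 to 24 per arm would do. The documents do not say which is meant.

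**2. Power of B versus C.** Let C have 0.6 times the capsule rate and B 0.8 times, so that B has half of C's effect. With a capsule rate of 40% this is 32% v 24%: (0.08 − 1.96 × 0.0669)/0.0667 = −0.77, so power is 22%. Over capsule rates of 10 to 50% the range is 8 to 29%. For 80% power, 32% v 24% needs 494 per arm and 16% v 12% needs 1,181.

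**3. How often an order is seen or reached.** Simulation, at least 200,000 trials per scenario, 90 per arm:

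| True rates A/B/C (%) | Observed order is C<B<A | All three pairwise tests significant in that order |
|---|---|---|
| 30/18/18 (equal doses) | 43% | 0.2% |
| 40/24/24 (equal doses) | 45% | 0.5% |
| 55/33/33 (equal doses) | 47% | about 1% |
| 30/18/10.8 (C cuts a further 40%) | 87% | 6.5% |
| 40/24/14.4 (C cuts a further 40%) | 93% | 16% |
| 55/33/20 (C cuts a further 40%) | 97% | 38% |

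In the half-effect case, the pattern with C versus A significant and the other two pairs not occurs in 27% of trials at 40/32/24% and 23% at 30/24/18%. The SAP has no reading for it.

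**4. What the data can say about C minus B.** With both rates equal to p, half-width = 1.96·√(2p(1−p)/90). At p = 24%: 1.96 × √(0.3648/90) = 12.5 points. At 12, 18 and 33% it is 9.5, 11.2 and 13.7 points.

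**5. Pooling B and C (180) against A (90).** Equal doses at 0.6 times the capsule rate, power in percent:

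| Capsule rate | 20% | 30% | 40% | 50% |
|---|---|---|---|---|
| One pessary arm v A | 31 | 47 | 64 | 79 |
| Three-arm test | 32 | 50 | 68 | 83 |
| Pooled v A | 42 | 61 | 77 | 89 |

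The gain over the three-arm test is 10, 11, 9 and 6 points. If only the higher dose works (40/40/24%), power is 26% pooled, 66% for the three-arm test and 64% for C versus A.

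**The case against.** The strongest reply is that the SAP asserts nothing in advance. The order is only expected, it is to follow from the results, B versus C is tested directly, and the study is exploratory. Each of these is true. They do not supply a rule for claiming an order or an estimate of the dose difference, and exploratory status is itself a reason to estimate rather than to establish.

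A reader might infer more than the documents support:

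- **That the planned tests cannot rank the doses.** The comparison exists. It has low power and no decision rule.
- **That the ranking is a coin toss.** This holds only for equal or nearly equal doses with the order read from point estimates. With half the effect at the lower dose, the two doses are observed in the right order in 65 to 87% of trials (capsule rate 10 to 40%).
- **That not pooling wastes 7 to 14 points of power.** That figure needs equal doses, a 40% relative reduction, a capsule rate of about 10 to 55%, and a single pairwise test as comparator. Against the three-arm test, which the SAP runs first, the gain is 6 to 11 points. Against significance for either dose at unadjusted 0.05 there is no gain (45.2% v 42.5% pooled at a 20% capsule rate), although unadjusted testing has its own price: under no difference, at least one of three ungated pairwise tests is significant in 12 to 13% of trials.
- **That the SAP defers pooling until results are known.** The conditional phrase is in Protocol 9.2. It lacks a criterion, but it does not say when the choice is made.

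The assumed rates are also open to challenge. SAP section 10 analyses deliveries between 32 and 34 weeks, and that proportion cannot exceed the one for all deliveries before 34 weeks. Lower rates would weaken the B versus C test further.

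**Conclusion.** The point holds as a fault of conclusion, and it should be corrected. The SAP promises an order of treatments, yet the step that separates the doses is unsized, has 8 to 29% power when the lower dose has half the effect, and carries no planned interval. Read from point estimates, the expected order appears in 43 to 47% of trials with equal doses. Read from significance, it is reached in about 1% or fewer with equal doses and in 6 to 38% under a large true dose effect.

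These figures rest on 90 evaluable women per arm and on assumed capsule rates of 30 to 55% (10 to 50% for the B versus C power), because the documents state none for sizing. That no ordering rule and no B versus C estimate are given is plain from the text and needs no assumption. The documents do not support a general claim that the doses cannot be compared, or that the planned tests should give way to a pooled contrast.

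**What to change.** In SAP section 10:

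1. Delete the transitivity sentence, and delete the expected order as a conclusion.
2. Report C minus B as a risk difference with a 95% CI, for estimation only. State that a non-significant B versus C result does not show the doses to be equal.
3. Give risk differences with 95% CIs beside the odds ratios for B and C against A.
4. Keep the three-arm test, C versus A and B versus A as planned.

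Optionally, replace the conditional pooling phrase in Protocol 9.2 with a named supportive analysis of B and C together against A. It should neither replace nor gate the planned tests, since it gains power only if the doses are about equal and loses it if only the higher dose works.

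While the section is open, two inconsistencies there need reconciling. The null hypothesis and the alternative give different figures for the higher dose (7.7 and 7.3). The text on B versus C also speaks of fewer low-risk pregnancies under C, which runs against the displayed order.

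The cost is wording in the SAP, one optional phrase in the protocol and a few added table columns. Sample size, data collection and conduct do not change. What is given up is the option of announcing a ranking.

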## **9 STATISTICS**

This project aims to conduct a randomized, open-label, controlled, clinical-exploratory phase II study evaluating the efficacy of a cerclage pessary containing one of 2 doses of sustained-release micronized progesterone for prevention of preterm birth, compared to the treatment method currently used by obstetrics-gynecology specialists, which comprises the administration of one daily capsule by vaginal route of 200 mg of progesterone. A total of

270 pregnant participants at risk of preterm birth will be enrolled, screened, and randomized to the 3 groups of treatment previously described. The number of patients listed ( $n = 270$ ) refers to the number of patients who effectively are enrolled and successfully complete the study. Therefore, an enrollment of at least 10% over that number (27 patients or more) should be considered due to the eventual withdrawal or early loss to follow-up of patients initially recruited.

As primary results, the proportions of spontaneous preterm delivery before gestation weeks 32 and 34 will be compared between the control group and the 2 groups with the pessaries containing different doses of progesterone. The risk of spontaneous preterm birth from the time of inclusion in the study through the gestation weeks 32 and 34 will be determined by a Kaplan-Meier analysis, where gestational age will be the time scale and spontaneous delivery will be the event; elective parturitions will be censored. For the purpose of this analysis, pregnancies will no longer be considered as high risk for the event if delivery occurs at the week of gestation 34 (34 0/7) or beyond.

As secondary outcomes, those qualitative variables in pregnant participants at risk of preterm birth will be evaluated, and the percentage distribution of acceptability responses or side effects recorded will be determined. For the quantitative variables (measurements of length and cervical angulation), the averages and standard deviations of the values found will be compared. Accordingly, each participant will work as her own control.

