this is in terms of decrease of the proportion of pregnancies with premature risk. In this way it will be determined the effective response to progesterone in the cerclage pessary through the occurrence of spontaneous delivery after 32 weeks but before 34 weeks of gestation. The evaluation of the error type 1 will be with a value of 0.05 for the type of variable being used.

As part of the exploratory analysis for the efficacy of treatments, the risk of spontaneous premature birth from the moment of inclusion in the study until the weeks 32 and 34 of gestation, will be determined with the Kaplan-Meier analysis, where the gestational age is the timeline, spontaneous delivery will be the event and elective deliveries will be censored. A singleton pregnant subject between 16 and 24 weeks of gestation will be eligible to participate in the study when she meets one of the following two conditions:

- Cervical length between 10 to 25 mm and without risk factors
- Cervical length greater or equal to 10 mm and with pre-existing risk factors in the immediate preceding pregnancy characterized by:
 - premature delivery before the week 35 (with a viable fetus)
 - premature rupture of membrane prior to week 35 (with a viable fetus)

There are two ways to measure the gestational age which are the following:

- Gestational Age according to DLNM (weeks)
- Gestational Age according to Transvaginal Ultrasound (weeks)

The time of gestational age will be evaluated through log-rank tests among treatments. The null hypothesis is stated as the no treatment differences in the gestational ages.

Kaplan-Meier (product limit) estimates of the gestational age distribution will be calculated and their corresponding 95% confidence interval (CI) will be presented: 25th percentile, mean, median, and 75th percentile.

The analysis will be performed for the two measurements of gestational time, considering the Transvaginal ultrasound the one most accurate.

For the purposes of this analysis, pregnancies will no longer be considered of high risk in the event birth takes place in week 34 (34 0/7) of gestation or more.

SECONDARY ANALYSIS

For some of the secondary variables, subjects will be their own controls in the following variables to evaluate and the following analysis are proposed:

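### SAP section 10 runs three pairwise dose comparisons at 0.05 with no stated gate, so the chance of at least one false-positive pair is about 12%; one sentence tying them to the overall test brings it to about 5%

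*SAP*

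**What the plan says.** SAP section 5 sets a general rule: "Two tailed test will be carried out for all the analysis and the type I error is 0.05". Section 10 repeats it for the primary analysis: "The evaluation of the error type 1 will be with a value of 0.05".

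The tests in section 10 come in this order:

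1. An overall comparison of the proportions, "among treatments through the CMH test".
2. C versus A, as the second step, "with the intention to confirm the significant difference between the highest dose and the standard treatment".
3. B versus A: "Afterwards, the same comparison of proportions will be done with treatment B in order to establish the difference".
4. B versus C, hoping to show superiority.

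The SAP then expects to rank the treatments, with C best and A worst. The formal hypotheses in the same section concern only B and C against A.

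The SAP's endpoint is one window, spontaneous delivery after 32 but before 34 weeks. The protocol, which the SAP names as the final reference, has two cut-offs in section 9: "the proportions of spontaneous preterm delivery before gestation weeks 32 and 34 will be compared between the control group and the 2 groups". It does not say which one leads.

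Neither document contains a gate, an alpha split or any other multiplicity rule. Both describe the study as exploratory phase II.

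**The concern.** An order of performing tests is not a testing hierarchy. As section 10 stands, a non-significant overall test does not stop a claim for C versus A, and a failed C versus A does not stop a claim for B versus A or B versus C. Each test has its own 5% chance of a false positive, and the dose conclusion draws on all of them.

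The protocol's primary outcome is determination of the effective dose, and the SAP means to reach it by significance and ranking. A chance result in one pair could therefore feed a wrong dose conclusion while the report cites a type I error of 0.05.

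**Working it through.** **Inputs.** From the documents: three arms with 90 analysed per arm (Protocol 9.1; SAP section 3), two-sided 0.05, uncorrected chi-square. The CMH test with no strata is practically the same test. Neither document gives a control event rate, so event rates below are assumptions, shown as ranges.

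**1. The plan's own figure.** For a single comparison (C versus A), simulated null trials with 90 per arm give 4.2% to 5.2% for event rates of 5% to 40%. So 0.05 reproduces as a per-test level.

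**2. Three pairs, one endpoint, large-sample.** With three equal arms, some pair has |z| > 1.96 exactly when the range of three independent standard normals exceeds 1.96 × √2 = 2.77. The studentized range distribution (k = 3, infinite df) gives 12.2%. Three independent tests would give 1 − 0.95³ = 14.3%; the pairs share arms, so the true figure is lower.

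**3. The same with binary data, 90 per arm.** Simulated trials with equal true rates:

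| Assumed event rate | Any of 3 pairs, no gate | Any of 3 pairs, overall test required | Listed order made binding |
|---|---|---|---|
| 5% | 10.0% | 4.3% | 4.2% |
| 10% | 12.2% | 4.8% | 5.0% |
| 20% | 11.9% | 5.0% | 4.9% |
| 40% | 12.7% | 5.0% | 5.2% |

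This applies to any single binary endpoint, whether the SAP window or one protocol cut-off.

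**4. Only the two pessary-control pairs.** Large-sample 9.0%; 8.0% to 9.4% at assumed rates of 6% to 40%. Two independent tests would give 1 − 0.95² = 9.75%. This is the figure matched to the SAP's formal hypotheses.

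**5. Pessary-control pairs at both protocol cut-offs (four tests).** Births before 32 weeks are a subset of births before 34, so the tests are correlated. Assumed rates before 32 / before 34 weeks, 90 per arm:

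| 3/6% | 5/10% | 6/15% | 10/15% | 10/20% | 20/40% | 5/40% |
|---|---|---|---|---|---|---|
| 13.5% | 14.0% | 14.5% | 13.9% | 15.1% | 15.7% | 16.0% |

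Letting the before-34 rate run from 5% to 40%, and the share of those births before 32 weeks from 30% to 80%, widens this to about 11% to 17%.

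**6. Why the gate works with three arms.** If all arms are equal, nothing is claimed unless the overall test is significant, so the error is at most about 5% (third column of the table in step 3). If one arm differs from the other two, only one pairwise null is true, and it is tested at 0.05. No other null configuration exists.

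**7. Cost in power.** The stated 80% with 90 per arm is reached for a 40% relative reduction only at a control rate of about 51% (51% × 0.6 = 30.6%). At those assumed rates, with only the 6.3 g pessary effective, power for B versus A is:

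| Rule | Power for B versus A |
|---|---|
| No gate | 80% |
| Overall test as gate | about 76% |
| Order C-A, B-A, B-C binding | about 3% |

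For comparison, Bonferroni over three tests (0.05/3 = 0.0167) gives an error of 4.4% but power of 65.5%, or 121 per arm to restore 80%.

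**The case against.** The strongest reply is that this is an exploratory phase II study, for which family-wise control across arms is not automatically required, and that 0.05 in sections 5 and 10 reads most naturally as a nominal level for each test. Both points stand: the SAP makes no family-wise claim that could be called false. They do not remove the issue. Section 10 speaks of confirming a significant difference and ranks the doses, and it attaches the exploratory label specifically to the Kaplan-Meier analysis. If 0.05 is only per test, the plan states no error rate for its dose conclusion.

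A second reply is that the overall CMH test comes first and so protects the rest. It would, but only as a required gate, and no sentence makes it one.

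Two stronger readings are tempting and should be resisted:

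- A reader might combine the SAP's three pairs with the protocol's two cut-offs and infer six tests and an error of some 18% to 21%. No passage specifies that combination. The SAP has three pairs at one window; the protocol's primary comparison is pessaries against control at two cut-offs.
- A reader might infer that any false positive could be reported as an effective dose. B versus C alone cannot show that a pessary works, nor can a result favouring capsules. The chance that either pessary falsely beats capsules is about 4% to 5% at one cut-off and 7% to 8% at two.

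**Conclusion.** The plan is missing a decision rule. With all arms equal and each test read at 0.05, the chance of at least one false-positive pair is about 12% (10% to 13% over assumed event rates of 5% to 40%), and about 9% for the two pessary-control pairs. The large-sample 12.2% rests on nothing beyond equal arms and the stated 0.05. Testing those two pairs at both protocol cut-offs gives about 11% to 17%; this range rests wholly on assumed rates and applies only if the protocol's endpoint is the one used.

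The documents do not support saying that a claimed family-wise 5% is really 12% or more, because no family-wise claim is made. They do support saying that dose claims worded as confirmation rest on tests whose joint error rate is neither stated nor controlled. Exploratory status lowers the weight of the point, but it is still worth correcting because the correction is so cheap.

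**What to change.** In SAP section 10, add a sentence to this effect: *Pairwise significance claims (C versus A, B versus A, B versus C) will be made only if the overall three-group CMH test on the lead endpoint is significant at two-sided 0.05; otherwise the pairwise results are reported as odds ratios with 95% confidence intervals.* No extra patients are needed. The cost is about four points of pairwise power (80% to 76% at the assumed 51% versus 30.6%).

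Making the listed order binding is an alternative that also gives about 5% and leaves C versus A at its full 0.05. Its downside is that no claim for 6.3 g could follow a failed 7.7 g comparison, which is a real loss in a study meant to determine the effective dose.

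Separately, reconcile the SAP's window (after 32 but before 34 weeks) with the protocol's cut-offs (before 32 and before 34 weeks), and name one lead endpoint. Report any other with odds ratios and 95% confidence intervals only. The gate controls the error for one endpoint, so this step is needed for the 5% to hold.
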